3.2 Study Schematic

Patients will be randomized (1:1 ratio) to receive IVIG or placebo (normal saline). The IVIG or placebo dose will be determined based on ideal weight with a dose not to exceed 80 grams. Patients will be given 650 mg acetaminophen (Tylenol®) and Diphenhydramine (Benadryl®) 25 mg PO PRN, may repeat once after 30 minutes if ineffective, 30 minutes prior to IVIG or placebo administration at every infusion. Patients will receive IVIG or placebo (0.5g/kg) daily for 1 day [week 1 day 1], then they will receive IVIG or placebo (1g/kg not exceeding 80g) daily for 1 day [week 1 day 2]. Patients will also receive 500 ml normal saline before and after the higher dose infusion of 1g/kg. Then, once every 2 weeks [week 3 & 5], patients will receive (0.6g/kg) IVIG or placebo for 4 weeks (2 infusions). After completion of all 4 infusions all patients will be again evaluated at Mayo Clinic [week 6].

The primary aim is to demonstrate the efficacy of IVIG relative to placebo in reducing or stopping seizures [$\geq 50\%$ reduction in seizure frequency] in patients with VGKC Ab associated autoimmune epilepsy. At the end of the 5 week trial, all patients in the initial placebo group (n=15) will receive, in an open label fashion with the same premedications and prehydration protocols IVIG. To help speed up the transition for the placebo group, 1 person from the Mayo study staff, not in direct contact with patients or assessment procedures, will be unblinded, to allow for scheduling with Option Care for the future home infusions. Mayo study staff will work with Option Care to get the IVIG infusions scheduled for the placebo group as soon as possible after the patient's 6 week visit to Mayo Clinic. Option Care home infusion agency will administer these patients IVIG (0.5g/kg) 1 day [week 7 day 1] then IVIG (1g/kg not exceeding 80g) for 1 day [week 7 day 2], then once every 2 weeks for 4 weeks (0.6g/kg IVIG) [week 9 and 11]. After completion of all 4 IVIG infusions these 15 patients will be again evaluated at Mayo Clinic [week 12].

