All patients will receive phone calls from the clinical research coordinator at 2 weeks, 4 weeks to assess patient reported side effects and record seizure diary information. The placebo group that will receive IVIG in an open label fashion, will also receive phone calls every week (weeks 7-11) to assess patient reported side effects and record seizure diary information. Any side effects or increase in seizure frequency from previous baseline will be reported to the principal investigator or designee to determine if any action should be taken or if un-blinding is required. Patients will also be given 24 hour emergency contact information for the study team to carry with them at all times.

Treatment location:

First 4 infusions will be given at Mayo Clinic using Mayo's standard operating procedures for infusion administration (see appendix 1). This will allow study personnel to closely evaluate the patient and give the home care network time to set the home treatment.

Home infusions:

The 4 IVIG infusions for those 15 initial placebo group patients will be given at the patient's home or clinic near their home. These infusions will be given per Option Care's standard operating procedure (see appendix 2)

In this study we are going to utilize the home care network of Option Care nationwide. Therefore one of the inclusion criteria is that the home treatment network is available where the patient lives.

Our secondary aim firstly investigates clinical factors predictive of IVIG response. These will include antibody type (LGI1, CASPR2, other) and titer. Thus blood draws will be performed at baseline, 6 weeks and 12 weeks (for placebo only). Secondly, we will assess for improvements in cognitive performance as measured by the KOKMEN¹⁷ and the Repeatable Battery for the Assessment of Neuropsychological Status (RBANS).²⁰

Our tertiary aim, a clinical observational study, investigates factors influencing relapse rate after a positive IVIG response. "Responders" from AIM 1 will be randomly assigned in open label fashion by the treating physician to 2 clinical observational groups:

- Immunotherapy (as per physician/insurance approval): mycophenolate mofetil 2000mg daily or azathioprine 2mg/kg +/- IVIG taper or IVMP taper
- No immunotherapy

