3.3 Primary Study Endpoints

Reduction of 50% or more, in seizure frequency with IVIG treatment.

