7.1 Statistical Methods

Dr. [REDACTED], senior statistician and Professor of Biostatistics, will be responsible for analyzing study data. The treatment (IVIg or placebo) will be unblinded at the 6 week follow up.

Randomized Placebo Controlled Trial:

The study will include 30 patients (15 per arm). Data collected will be summarized using descriptive statistics such as mean, standard deviation, median, minimum and maximum for continuous variables and using frequencies and percentages for categorical variables (see Study Endpoints). Primary outcome, which is binary variable, i.e. proportion of patients responding to treatment (yes, no) will be estimated along with 95% exact binomial confidence intervals for each arm of the respective study. These proportions will then be compared using Fisher's exact test within the study. Continuous outcomes of interest will be compared using two sample t-test or Wilcoxon rank sum test as appropriate.

Multiplicity

Due to smaller sample sizes, no adjustment for multiple comparisons is done.

Power/Sample Size

Sample size and power calculations for various scenarios using Nquery advisor software version 7.0 are provided below.

VGKC complex antibody positive

Based on preliminary data, assuming 70% responders on IVIG vs. 10% on Placebo, a total sample size of 30 (i.e.15 per group) will have 89% power at an alpha level of 5% using Fisher's exact test.

Dropouts

If we assume a maximum dropout rate of 20%, we would still maintain >80% power. In an event if the dropout rate exceeds anticipated rate, we would still have 82% power to detect hypothesized difference (70% versus 10%) with as few as 12 patients per group.

Effect of patient enrolment on power analysis in Randomized Placebo Controlled Trial

Group 1: Assuming the rate of positive response to IVIG and placebo is 70% and 10%, respectively:

Two group Fisher's-exact test of equal proportions (odds ratio = 1) (equal n's)

	1	2	3	4
Power (%)	82	89	94	97
n per group	12	15	17	19

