7.2 Endpoints

Primary endpoints*

- 1) Change in seizure frequency

The definition of a “responder” is a patient with a $\geq 50\%$ reduction in seizure frequency.

Secondary endpoints

Clinical factors predictive of immunotherapy response.

The following clinical factors will be analyzed with respect to prediction/correlation with favorable outcome.

- 1) Interval from symptom onset to immunotherapy treatment
- 2) Type of onset
- 2) Clinical course
- 3) Seizure type and frequency
- 4) EEG abnormalities
- 5) Presence of other neurological symptoms or signs (tremor, headache, myoclonus)
- 6) CSF findings (White cell count; protein)
- 7) Neural autoantibody type (LGI1, CASPR2, other) and titer (blood draws will be performed at baseline, 6 weeks and 12 weeks (for placebo group only)
- 8) Change in The Repeatable Battery for the Assessment of Neuropsychological Status (RBANS) scale scores

Tertiary endpoints

For the 1 year follow up “observational study”

- “Responder” patients from Trial will be randomly assigned to 2 clinical groups:
 - Immunotherapy (as per physician/insurance approval): mycophenolate mofetil 2000mg daily or azathioprine 2mg/kg +/- IVIG taper or IVMP taper
 - No immunotherapy
- Subjects will be followed for relapse for a total of 12 months (see study schedule of events).
- Patients will keep a daily seizure diary and record any adverse events while on immunotherapy.
- The study coordinator will call patients every month review seizure history and adverse events.
- Patients will be seen at 6 months and 12 months as part of standard clinical care-neurological examination will be recorded.
- Relapse will be defined as $\geq 20\%$ increase in seizure frequency compared with post IVIG frequency.
- Cognition will be assessed by the study coordinator who will perform Telephone Interview for Cognitive Status and the KOKMEN at each monthly call.
- If relapse occurs, the patient will be seen at the clinic. Patients on no therapy will be started on immunotherapy, those on therapy will have treatment adjusted as per current standard clinical care.

8 Safety and Adverse Events

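### Small sample size is no reason to waive multiplicity control: the secondary analyses need a testing order or an exploratory label, while the primary test is unaffected

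*Combined protocol and SAP*

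**What the plan says.** Section 7.1, under Multiplicity, consists of one sentence: "Due to smaller sample sizes, no adjustment for multiple comparisons is done".

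The same section sizes the trial on the primary outcome alone. It does so by "assuming 70% responders on IVIG vs. 10% on Placebo", and concludes that "a total sample size of 30 (i.e.15 per group) will have 89% power at an alpha level of 5% using Fisher's exact test". This is the only place where a significance level appears.

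Section 3.3 gives a single primary efficacy endpoint: "Reduction of 50% or more, in seizure frequency with IVIG treatment".

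The secondary material is spread over four places:

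- Section 2 makes two questions formal secondary aims: which clinical factors predict response, and whether IVIG improves RBANS by at least 20%.
- Section 3.4 names the 20% RBANS improvement as the secondary endpoint.
- Section 3.2 says "Secondly, we will assess for improvements in cognitive performance" and names KOKMEN beside RBANS as the measures.
- Section 7.2 places the predictors under secondary endpoints: "The following clinical factors will be analyzed with respect to prediction/correlation with favorable outcome". Nine lines follow (the number 2 is used twice). The last is change in RBANS scores.

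For the predictor analyses the plan gives no test, model, significance level or analysis population. For the secondary analyses as a whole it gives no testing order and does not call them exploratory.

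**The concern.** The chance of a false positive over a set of tests depends on how many tests there are, the level of each, and how they are related. The number of patients does not enter, except that exact tests on small groups often run below their nominal level. What a small sample does change is power. A predictor that reaches significance in 30 patients is then more likely to be a chance result, or an exaggerated one, than in a larger study.

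Small numbers can be a reason not to spend power on adjustment. If so, the matching step is to say that the unadjusted analyses support no firm claim, and the plan does not say that. As written, a predictor or a cognitive benefit could be reported as an answer to a formal secondary aim without the reader knowing how many comparisons lay behind it. The cognitive question is especially open. RBANS appears as a 20% threshold in sections 2 and 3.4 and as a change score in section 7.2, and KOKMEN is a second scale.

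**Working it through.** **1. The plan's own figure.** Inputs from section 7.1: response rates 70% and 10%, 15 per group, 5% level, Fisher's exact test. Sidedness is not stated. Method: sum the two binomial probabilities over every pair of responder counts for which the two-sided Fisher p-value is at most 0.05.

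| n per group | stated power | recomputed |
|---|---|---|
| 12 | 82% | 82.6% |
| 15 | 89% | 89.4% |
| 17 | 94% | 94.8% |
| 19 | 97% | 97.5% |

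The stated figures are reproduced, so the primary test is a single two-sided 5% test. A one-sided 5% test would give 95.0% at 15 per group, which does not match. One endpoint tested once needs no adjustment.

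**2. Counting the secondary variables in section 7.2.** Interval from onset 1, type of onset 1, clinical course 1, seizure type and frequency 2, EEG 1, other signs 3 (tremor, headache, myoclonus), CSF 2 (cells, protein), antibody 2 (type, titre), RBANS change 1.

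1 + 1 + 1 + 2 + 1 + 3 + 2 + 2 + 1 = 14 variables on 9 lines.

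RBANS change is already among the 14. Adding KOKMEN makes 15. The count is 16 only if RBANS is tested both as a correlate of response and as a treatment effect.

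**3. Upper figure.** Assume 5% per test, independent tests and every null hypothesis true. The chance of at least one false positive is 1 − 0.95^k:

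- k = 9: 1 − 0.630 = 37.0%
- k = 14: 1 − 0.488 = 51.2%
- k = 15: 53.7%
- k = 16: 56.0%

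The expected number of false positives with 14 tests is 14 × 0.05 = 0.70.

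**4. Correlated tests.** The listed factors are unlikely to be independent. The documents give no correlations, so these are assumed: normal test statistics with a common pairwise correlation, by simulation.

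| tests | 0 | 0.3 | 0.5 | 0.7 |
|---|---|---|---|---|
| 9 | 37% | 33% | 27% | 20% |
| 14 | 51% | 44% | 35% | 25% |

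**5. Conservative exact tests.** Fisher's test between 21 responders and 9 non-responders (30 patients at 70% response) has a true level of 1.1% to 3.9% when the factor's prevalence is 10% to 50%. A simulation of 14 independent tests (8 Fisher at an assumed 40% prevalence, 6 Wilcoxon) gives:

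- 30 patients, 70% response: 44%
- 15 patients, 70% response: 36%
- 30 patients, 90% response: 28%

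With 15 patients and one non-responder, no test can reach 5%. The smallest Fisher p-value is 1/15 = 0.067.

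**6. Effect of a fix on the primary test.** A sequence that starts with the responder comparison at 5% leaves that test as it is, so the stated 89% power stands.

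**The case against.** The strongest reply is that the plan nowhere says that 14 tests will be run at 5% each. The level is stated only for the primary outcome, and section 7.2 speaks of prediction or correlation without naming a test. That is correct, so the percentages above describe one reasonable reading of an unspecified analysis. A reader might infer that the plan will produce a false claim about half the time, but the documents do not support this. It needs a 5% level, independence, every compound line split and every null true.

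The all-null assumption is also severe. Section 1.1 reports earlier associations, in the group's cognitive-disorder series, for about seven of the 14 variables: onset, course, tremor, delay to treatment, CSF protein, CSF cells and antibody type. If only the other seven were null, the figure would be 1 − 0.95^7 = 30%. That series is a different population, so this is illustrative, but it does pull the figure down.

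A reader might also infer that secondary findings would carry the same standing as the primary result. The documents do not say so. They separate primary, secondary and tertiary aims and power only the primary. The statement in the background section about informing later studies is conditional on a definite IVIG benefit, so it concerns efficacy and not predictors. Likewise, RBANS is already placed ahead of KOKMEN, because only RBANS is named in the secondary aim, in section 3.4 and in section 7.2.

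Section 4.3 expects 80–100% response, and few non-responders would lower the false-positive rate. That is true, but it does not rescue the analysis: the rate falls because almost nothing can then be established, which is itself a reason to report estimates only.

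Finally, the waiver can be read as an open choice to protect power. On that reading an exploratory label is still missing.

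**Conclusion.** The concern holds in a limited form. The stated reason does not justify the waiver, and the secondary aims have neither a testing order nor an exploratory label. The primary conclusion is not inflated, and its stated 89% power is reproduced.

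The size is an upper range: up to 37% for the nine listed lines and 51% for the 14 split variables, if each is tested at 5% and the tests are independent with all nulls true. It is about 25–44% for 14 tests at assumed correlations of 0.7 to 0.3, and about 28–44% in the simulated small-sample cases, leaving aside the case where no test can reach 5%. The level, correlations, prevalence and the response split of 90% are assumptions. Even the lower end is high for secondary claims that carry no label. The matter is worth correcting because the correction is cheap. It does not threaten the trial's main result.

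**What to change.** Replace the Multiplicity sentence in section 7.1 with text to this effect:

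> Confirmatory testing follows a fixed sequence. (1) Responder proportions are compared between arms at the 5% level. (2) Only if (1) is significant, the proportion with at least 20% improvement in RBANS (section 3.4) is compared between arms at week 6 at the 5% level. The RBANS change score is supportive. KOKMEN, all predictor analyses and all tertiary analyses are exploratory and are reported as estimates with 95% confidence intervals. No predictor or effect will be described as established on the basis of these analyses.

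Naming the RBANS analysis matters, because the plan currently allows either the threshold or the change score. Week 6 is the natural time point: section 6.14 schedules RBANS in both arms at that visit, and under section 6.5 unblinding and open-label IVIG for the placebo arm come after it.

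The cost is a few sentences and no new data. The primary test keeps its level and its stated 89% power, and the sequence holds the error over the two confirmatory tests at 5%. The downside is that no confirmatory RBANS claim can be made if the responder comparison fails. The plan gives no expected RBANS rates, so the power of step (2) cannot be stated from the documents.

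### The 82% power quoted for dropout above 20% is the power at exactly 20% dropout (12 per group); the plan gives no power beyond that

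*Combined protocol and SAP*

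**What the plan says.** All the relevant text is in section 7.1 (Statistical Methods).

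- **Size:** "The study will include 30 patients (15 per arm").
- **Power at full enrolment:** "assuming 70% responders on IVIG vs. 10% on Placebo, a total sample size of 30" (15 per group) is given "89% power at an alpha level of 5% using Fisher's exact test".
- **Dropouts, first sentence:** "If we assume a maximum dropout rate of 20%, we would still maintain >80% power".
- **Dropouts, second sentence:** "In an event if the dropout rate exceeds anticipated rate, we would still have 82% power to detect hypothesized difference". It goes on to repeat the two response rates and ties the figure to a group size: "with as few as 12 patients per group".
- **Power table:** 82, 89, 94 and 97% at 12, 15, 17 and 19 per group. The caption specifies equal group sizes, and no row lies below 12.

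**The concern.** The second Dropouts sentence is the plan's only statement about dropout worse than expected. It reads as a calculated reserve: even if the 20% allowance is exceeded, power is still 82%. But the group size it names is what remains when the allowance is exactly used up. The two sentences therefore describe the same case, and the second presents it as a worse one.

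If so, the plan contains no calculation for dropout above 20%. An ethics board or funder reading the paragraph would believe there is a margin that was never worked out. In a trial of 30, a few extra losses can matter, so it is worth knowing what power would actually be there.

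**Working it through.** **Inputs, all from section 7.1:** 15 per arm; responder rates 0.70 (IVIG) and 0.10 (placebo); Fisher's exact test; alpha 5%; maximum dropout 20%. Whether the test is one- or two-sided is not stated, so step 1 settles it from the plan's own figures.

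**Assumptions not in the plan:** dropouts are left out of the analysis, and dropout is unrelated to response. For unequal splits, dropouts fall at random over the 30 patients.

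**Formula.** With n₁ patients on IVIG and n₂ on placebo,

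power(n₁, n₂) = Σₐ Σ_b Bin(a; n₁, 0.70) × Bin(b; n₂, 0.10) × 1[Fisher p(a, b) ≤ 0.05],

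summed over every possible pair of responder counts a and b.

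**Step 1: reproduce the plan.**

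| n per group | Plan | Two-sided Fisher |
|---|---|---|
| 12 | 82% | 82.6% |
| 15 | 89% | 89.4% |
| 17 | 94% | 94.8% |
| 19 | 97% | 97.5% |

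The plan's figures are these values with the decimals dropped. A one-sided test gives 92.0% at 12 and 95.0% at 15, which does not match. The plan therefore used the two-sided test, and its figures are correct for their group sizes.

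**Step 2: match group size to dropout.** 15 × (1 − 0.20) = 12 per group, or 6 dropouts of 30. Dropout above 20% means at least 7 of 30, leaving at most 23 patients. Two groups of 12 need 24. Dropout above 20% and 12 in each group cannot both hold.

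**Step 3: power beyond 20%, equal groups (the basis of the plan's table).**

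| n per group | Dropout | Power |
|---|---|---|
| 12 | 20.0% | 82.6% |
| 11 | 26.7% | 75.5% |
| 10 | 33.3% | 66.7% |
| 9 | 40.0% | 67.5% |

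Power of an exact test moves in steps, so the decline is not smooth.

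**Step 4: power beyond 20%, random split between arms.** For D dropouts in total, k of them on IVIG, each split has weight C(15, k) × C(15, D − k) / C(30, D). Average power is Σₖ weight × power(15 − k, 15 − D + k).

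| Dropouts of 30 | Rate | Average power | Range over single splits |
|---|---|---|---|
| 6 | 20.0% | 85.1% | 82.0–88.3% |
| 7 | 23.3% | 84.6% | 76.6–86.6% |
| 8 | 26.7% | 79.2% | 66.3–84.3% |
| 9 | 30.0% | 78.8% | not tabulated |
| 10 | 33.3% | 72.2% | 61.3–76.7% |

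The average at 7 dropouts exceeds the 82.6% for 12 versus 12 because equal groups happen to be an unfavourable split at these sizes. At 7 dropouts the two nearest-to-equal splits give 86.6% (11 IVIG, 12 placebo) and 84.3% (12 IVIG, 11 placebo). At 8 dropouts the equal split, 11 and 11, gives 75.5%, against 79.0% for 10 IVIG and 12 placebo and 84.3% for 12 IVIG and 10 placebo.

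**Step 5: sensitivity to the definition of the p-value.** If the two-sided p-value is taken as twice the one-sided one, the equal-group results are unchanged, so the plan's table cannot tell the two conventions apart. The random-split averages fall to 77.3% at 7 dropouts, 75.9% at 8 and 69.3% at 10.

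**The case against.** The best defence is that no printed number is wrong. The sentence names its own limit of 12 per group, and the table directly below gives 82% there, so a careful reader can see where the assurance ends. One can also try to separate the two terms: if the anticipated rate is some lower expected figure and 20% is the ceiling, the sentence would cover the range between them, and 82% would be its correct lower end. Finally, on random-split averages the claim is still met at the first step past 20% (84.6% at 7 dropouts).

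Part of this stands. The power figures are correct, and on the usual two-sided p-value average power drops below 80% only from 8 dropouts. The separate-rates reading does not stand, because 20% is the only dropout rate in the documents. Naming 12 per group does not rescue the sentence either, because that group size is incompatible with the condition it is attached to.

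A further caution is fair. Section 7.1 does not say how dropouts are analysed, and sections 4.4.2 and 6.13 have withdrawn patients attend an early termination visit with diary review, so a withdrawal need not mean a missing outcome. Any power sentence that assumes exclusion should say that this is the basis of the calculation, not a rule for the analysis set.

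**Conclusion.** The concern holds. The 82% is the power at the anticipated maximum dropout, and the plan states none beyond it. With equal groups, power is 75.5% at 11 per group and 66.7% at 10. With random splits it averages 84.6% at 7 dropouts, 79.2% at 8 and 72.2% at 10.

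These figures rest on the plan's response rates, a two-sided Fisher test, and dropouts that are excluded and unrelated to response. Exclusion is what the plan's own use of 12 per group implies. If dropouts were instead counted as non-responders, the rates at 20% dropout would become 0.70 × 0.80 = 0.56 and 0.10 × 0.80 = 0.08 with 15 per arm, and power would be 73.1%.

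Severity is minor. The error lies in the scenario attached to a correct number, and sample size, test and alpha are unaffected.

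**What to change.** Replace the second Dropouts sentence in section 7.1 with:

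> Power is 82% at 20% dropout (12 per group). If dropout exceeds 20%, power with equal groups is about 76% at 11 per group and about 67% at 10 per group. These figures are calculated with dropouts excluded and dropout unrelated to response.

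Optionally add:

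> Averaged over random splits of dropouts between arms, power is about 85% at 7 dropouts in total, 79% at 8 and 72% at 10.

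If the optional sentence is used, name the definition of the two-sided p-value, since the averages depend on it.

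The cost is one sentence of section 7.1 rewritten and, if wanted, one added. Sample size, test, alpha and procedures stay as they are. The only consequence is that the stated power beyond 20% dropout becomes less favourable.
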